## Phase Ib Cohorts C0 and C1 DLT Definitions

DLT definitions reflect the known and expected toxicities of GDC-0810 administered alone and palbociclib administered alone or in combination with other endocrine therapies. A DLT is defined as one of the following toxicities occurring during the DLT assessment window and considered by the investigator to be related to GDC-0810 or palbociclib.

- Any Grade  $\geq 3$  non-hematologic, non-hepatic toxicity with the exception of:
  - Alopecia of any grade;
  - Grade 3 nausea, vomiting, or diarrhea that resolves to Grade  $\leq 2$  within 24 hours with maximal medical therapy
  - Grade 3 fatigue, unless the fatigue has increased by at least two grades from baseline
- Any grade non-hematologic toxicity that leads to study drug or study drug treatment interruption of  $> 7$  days' duration
- Grade  $\geq 3$  elevation of serum hepatic transaminase (ALT or AST) lasting  $> 7$  days
  - For patients with Grade  $\leq 2$  hepatic transaminase levels at baseline as a result of liver metastases, only a transaminase level  $\geq 10 \times$  ULN lasting for  $> 7$  days will be considered a DLT.
- Grade  $\geq 3$  elevation of serum bilirubin
- Any case of potential drug-induced liver injury that includes an elevated ALT or AST in combination with either an elevated bilirubin or clinical jaundice, as defined by Hy's Law as recommended in the U.S. FDA Guidance "Drug-Induced Liver Injury: Premarketing Clinical Evaluation," July 2009:
  - The finding of an elevated ALT or AST ( $> 3$  times baseline value) in combination, with either an elevated total bilirubin ( $> 2 \times$  ULN) or clinical jaundice in the absence of cholestasis or other causes of hyperbilirubinemia is considered to be an indicator of severe liver injury. Therefore, investigators must report as an adverse event the occurrence of either of the following:
    - Treatment-emergent ALT or AST  $> 3$  times baseline value in combination with clinical jaundice
    - Treatment-emergent ALT or AST  $> 3$  times baseline value in combination with total bilirubin  $> 2 \times$  ULN (of which  $\geq 35\%$  is direct bilirubin)

- Grade 4 febrile neutropenia of any duration
- Grade 4 neutropenia  $\geq 10$  days
- Grade 3 thrombocytopenia associated with clinically significant bleeding
- Grade 4 thrombocytopenia associated with:
  - $\geq 10$  days duration
  - Active bleeding
  - Requirement for platelet transfusion

- Grade 4 anemia

Note: In the event of a Grade 4 neutropenia, thrombocytopenia, or anemia, a complete blood count (CBC) must be performed at least on Day 5 after the onset of the event. If the absolute neutrophil count, platelet count, or hemoglobin has not recovered to  $\leq$ Grade 3, CBC should be rechecked again on or before Day 10. In order to define DLT, patients should not be prophylactically prescribed growth factor support prior to commencement of therapy (GDC-0810 and palbociclib).

- Grade 3 laboratory abnormalities that are asymptomatic and considered by the investigator not to be clinically significant will not be considered a DLT.

### **Phase Ib Cohort D1 Dose Safety Run-in DLT Definitions**

DLT definitions reflect the known and expected toxicities of GDC-0810 and LHRH agonists. A DLT is defined as one of the following toxicities occurring during the DLT assessment window and considered by the investigator to be related to GDC-0810 or LHRH agonists:

- Any Grade  $\geq$  3 non-hematologic, non-hepatic toxicity with the exception of:
  - Alopecia of any grade
  - Grade 3 nausea, vomiting, or diarrhea that resolves to Grade  $\leq$  2 within 24 hours with maximal medical therapy
  - Grade 3 fatigue, unless the fatigue has increased by at least two grades from baseline
  - Grade 3 premature menopause or Grade 3 hot flashes that resolve to Grade 2 with optimal medical management within 7 days
  - Grade 3 laboratory abnormalities that are asymptomatic and considered by the investigator not to be clinically significant will not be considered a DLT.
- Any Grade  $\geq$  3 hematologic toxicity of more than 7 days' duration
- Any grade toxicity that leads to study drug or study drug treatment interruption of more than 7 days duration
- Grade  $\geq$  3 elevation of serum hepatic transaminase (ALT or AST) lasting  $>7$  days
 

For patients with Grade  $\leq$  2 hepatic transaminase levels at baseline as a result of liver metastases, only a transaminase level  $\geq 10 \times$  ULN lasting for  $\geq 7$  days will be considered a DLT.
- Grade  $\geq$  3 elevation of serum bilirubin

- Any case of potential drug-induced liver injury that includes an elevated ALT or AST in combination with either an elevated bilirubin or clinical jaundice, as defined by Hy's Law as recommended in the U.S. FDA Guidance "Drug-Induced Liver Injury: Premarketing Clinical Evaluation," July 2009:

The finding of an elevated ALT or AST ( $>3$  times baseline value) in combination, with either an elevated total bilirubin ( $>2 \times \text{ULN}$ ) or clinical jaundice in the absence of cholestasis or other causes of hyperbilirubinemia is considered to be an indicator of severe liver injury. Therefore, investigators must report as an adverse event the occurrence of either of the following:

Treatment-emergent ALT or AST  $>3$  times baseline value in combination with clinical jaundice

Treatment-emergent ALT or AST  $>3$  times baseline value in combination with total bilirubin  $>2 \times \text{ULN}$  (of which  $\geq 35\%$  is direct bilirubin)

## **10.3 STUDY DRUG AND STUDY TREATMENT ADMINISTRATION**

The research staff at each participating site will provide detailed instructions and training for the handling of the study drug (GDC-0810) and study treatment (palbociclib and LHRH agonist) and their administration to each patient at the beginning of her study participation.

All patients should take the full prescribed dose of GDC-0810 by mouth at approximately the same time each day and within 30 minutes after eating a meal. GDC-0810 tablets should be swallowed whole and tablets should not be cut or crushed.

Evening dosing may be initiated to alleviate gastrointestinal symptoms from GDC-0810. Please note that morning dosing the day before PK evaluation days is required to allow accurate assessment of PK trough levels of study drug (see [Appendix 1](#), [Appendix 2](#), [Appendix 3](#), and [Appendix 4](#)).

If a dose is missed, patients should just take the next scheduled GDC-0810 dose, without compensating for the missed dose.

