## 1.2 CLINICAL PK SUMMARY

The clinical pharmacokinetics of GDC-0810 is under investigation in the ongoing clinical Phase Ia/Ila Study GO29642. Preliminary PK information from this study is summarized below.

- GDC-0810 was rapidly absorbed with peak concentrations achieved at 1–3 hours after dosing.
- The mean terminal half-life was approximately 8 hours, and mean apparent oral clearance was 8 L/hour after a single dose of GDC-0810 at 600 mg under the non-fasted condition. Consistent with the half-life, minimal drug accumulation was observed following multiple dosing.
- GDC-0810 exposure in the fasted state increased with dose across the entire dose range tested (100–800 mg).
- In the Phase Ia *portion of the study*, at 600 mg QD, mean $\pm$ SD steady state  $AUC_{0-6}$  and  $C_{max}$  for GDC-0810 was  $41.1 \pm 27.5 \mu\text{g} \cdot \text{hour/mL}$  and  $11.8 \pm 6.61 \mu\text{g/mL}$ , respectively, under the fasted state (n=6), and  $74.9 \pm 30.1 \mu\text{g} \cdot \text{hour/mL}$  and  $25 \pm 8.35 \mu\text{g/mL}$ , respectively, under the nonfasted state (n=5).
- In the Phase Ila *portion of the study*, at the RP2D of 600 mg QD under the fed state, mean $\pm$ SD steady state  $AUC_{0-6}$  and  $C_{max}$  for GDC-0810 was  $39.5 \pm 22.5 \mu\text{g} \cdot \text{hour/mL}$  (n=40) and  $14.3 \pm 7.3 \mu\text{g/mL}$  (n=42), respectively.

Based on pharmacodynamic (PD), clinical tolerability, and preliminary PK data collected to date, once-daily administration of 600 mg under fed conditions (within 30 minutes after eating a meal) was selected as the single-agent RP2D for GDC-0810. See the GDC-0810 Investigator Brochure for further details.

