### **10.3.1 Phase Ia**

During Phase Ia, the full prescribed dose of GDC-0810 should be taken by mouth in the morning, after fasting overnight, at approximately the same time each day; food should not be eaten for at least 1 hour after taking GDC-0810. The dosing regimen may be changed if the PK and safety data from the dose escalation suggest that a discontinuous regimen or another dosing frequency (e.g., BID), with or without a fasting requirement, may be preferable for the Phase IIa portion of the study.

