## **10.4 DOSE MODIFICATIONS**

Patients who have had treatment interruptions due to reasons other than DLTs may restart daily dosing at the same dose at the discretion of the investigator when the toxicity has resolved to Grade  $\leq 1$  or baseline; however, any patients whose treatment is interrupted for an adverse event that is related to study drug and who do not restart treatment within 28 days will be withdrawn from study treatment.

For patients experiencing a DLT, treatment should be held until the severity of the toxicity decreases to Grade  $\leq 1$  or baseline. If they are deriving clinical benefit, patients may be restarted on study drug at the next lower dose level that has been tested in a previous cohort, at the discretion of the investigator and in consultation with the Sponsor. For Phase Ia and Phase IIa, no more than 2 dose reductions of GDC-0810 will be allowed.

For Phase Ib Cohort C1 a maximum of two dose reductions of GDC-0810 and palbociclib will be allowed. No dose reductions are planned for the LHRH agonists (Cohort D1). GDC-0810 dose reductions should be managed without changing regimen, for example, patients in Phase Ia who were being treated on a BID regimen will dose reduce to the next lower GDC-0810 dose level but still administered as BID. Similarly, Phase Ia patients who were being treated without a fasting requirement will dose reduce to the next lower dose level but still administered without a fasting requirement.

Doses reduced for drug-related toxicity should generally not be re-escalated. However, intrapatient re-escalation back to the previous dose level may be permitted at the discretion of the investigator and in consultation with the Sponsor.

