**Table 4 Dose Modification and Management Guidelines**

Toxicity	Dose Modification and Management Guidelines
Gastrointestinal Toxicities:	
General	

• Patients should be closely monitored for gastrointestinal (GI) symptoms and their effects on their wellbeing. Patients experiencing nausea, vomiting, and diarrhea should be treated and managed per standard of care and per protocol guidelines, including use of anti-diarrheal agents and appropriate supportive care including hydration and dietary modification if clinically indicated.

• Remind patients to take GDC-0810 30 minutes after the largest meal of the day (preferably the evening).

Diarrhea:	
General	
At first report of any grade diarrhea:
 

• Initiate loperamide 4 mg, followed by 2 mg after each unformed stool. Daily dose should not exceed local recommendations in any 24-hour period.

• Infectious or alternate etiology should be excluded.

• Grade <math>\geq 2</math> diarrhea is identified as an AESI requiring expedited reporting from study sites regardless of seriousness.

Grade 1	

• Manage with adequate anti-diarrheal agents (e.g., loperamide) and maximum supportive care according to local standards and practices.

• Closely monitor for resolution.

• If diarrhea does not resolve after 14 consecutive days, hold GDC-0810 until complete resolution of diarrhea.

• Upon resolution, if Grade 1 diarrhea had persisted for > 1 week with no alternate etiology, consider starting loperamide 2 mg 1–2 times daily as secondary prophylaxis (i.e., use of loperamide to prevent further diarrhea).

AESI=adverse event of special interest

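### Phase Ia patients are given fed and fasted dosing instructions that cannot all be followed; how much this changes exposure is uncertain

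*Combined protocol and SAP*

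**What the plan says.** The administration instructions that reach a Phase Ia patient are these.

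- **Section 10.3 (general rule).** "All patients should take the full prescribed dose of GDC-0810 by mouth at approximately the same time each day and within 30 minutes after eating". The synopsis repeats this under Investigational Medicinal Products. Section 10.3 permits evening dosing for gastrointestinal symptoms and adds: "Please note that morning dosing the day before PK evaluation days is required to allow accurate assessment of PK trough levels of study drug". That sentence refers to Appendices 1 to 4, and Appendix 1 is the Phase Ia schedule.
- **Section 10.3.1 (Phase Ia).** "During Phase Ia, the full prescribed dose of GDC-0810 should be taken by mouth in the morning, after fasting overnight", and "food should not be eaten for at least 1 hour after taking GDC-0810". The synopsis repeats this in its Phase Ia paragraph. The notes to Table 7 return Phase Ia patients to fasted morning dosing after the FES-PET scan.
- **Table 4 (Section 10.4.1, headed for Phase Ia, Phase Ib Cohort D and Phase IIa).** Under gastrointestinal toxicities, general: "Remind patients to take GDC-0810 30 minutes after the largest meal of the day (preferably the evening").
- **Section 10.4 (dose reductions).** Regimen should be kept, and "Phase Ia patients who were being treated without a fasting requirement will dose reduce to the next lower dose level" still without that requirement. The same paragraph refers to Phase Ia patients on twice-daily dosing.
- **Appendices.** The dosing footnotes of Appendices 2, 3 and 4 state the post-meal condition. Footnote 9 of Appendix 1 states none.

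Section 7 allows Phase Ia patients with clinical benefit to continue on GDC-0810.

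**The concern.** A patient cannot take the same dose both after a meal and after an overnight fast, or both in the morning and preferably in the evening. A patient from a fasted cohort who follows Section 10.3 or Table 4 changes to fed dosing. A patient from the non-fasted 600 mg cohort (Section 3) who follows Section 10.3.1 changes to fasted dosing. Either can happen with no recorded change of dose.

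What is at stake is an unplanned change in exposure in continuing patients, and uncertainty at sites about what counts as compliant dosing. Section 14 lists an incorrect dose outside protocol specifications among protocol violations, so sites need one instruction to be held to.

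**Working it through.** **Step 1: does one rule clearly govern Phase Ia?**

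Two readings were tried.

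- *Section 10.3 governs everyone.* Section 10.3.1 and Table 7 are then wrong for Phase Ia.
- *Section 10.3.1 is a specific exception.* Two conflicts remain. Table 4 still directs fasted Phase Ia patients to post-meal dosing, preferably in the evening, in a section that names Phase Ia. And Section 10.3.1 covers all of Phase Ia, although Sections 1.2, 3 and 10.4 show that some Phase Ia patients were not fasted.

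Section 10.3.1 does allow the regimen to change, including the fasting requirement, but ties this to what may suit Phase IIa. It does not set a condition for the non-fasted Phase Ia patients. Neither reading removes the conflict.

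**Step 2: how much could meal condition matter?**

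The plan states no fed-to-fasted ratio, so there is no figure to reproduce. The inputs are the steady-state values in Section 1.2, all at 600 mg once daily:

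| Group | AUC0-6, mean ± SD (µg·hour/mL) | Cmax, mean ± SD (µg/mL) |
|---|---|---|
| Phase Ia fasted | 41.1 ± 27.5 (n=6) | 11.8 ± 6.61 (n=6) |
| Phase Ia non-fasted | 74.9 ± 30.1 (n=5) | 25 ± 8.35 (n=5) |
| Phase IIa fed | 39.5 ± 22.5 (n=40) | 14.3 ± 7.3 (n=42) |

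The simple measure is the ratio of arithmetic means. As a sensitivity check, assume log-normal exposure and independent groups. For each group, v = ln(1 + (SD/mean)²) and g = ln(mean) − v/2. The geometric mean ratio is exp(g₁ − g₀), with standard error √(v₁/n₁ + v₀/n₀) on the log scale and a Welch t interval.

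For AUC0-6, Phase Ia non-fasted against fasted:

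- v₁ = ln(1 + (30.1/74.9)²) = 0.150 and v₀ = ln(1 + (27.5/41.1)²) = 0.370
- g₁ − g₀ = 4.241 − 3.531 = 0.710, so the ratio is 2.03
- standard error = √(0.150/5 + 0.370/6) = 0.303 with 8.5 degrees of freedom, giving a 95% CI of 1.02 to 4.06

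| Contrast | AUC0-6: ratio of means | Geometric ratio (95% CI) | Cmax: ratio of means | Geometric ratio (95% CI) |
|---|---|---|---|---|
| Phase Ia non-fasted / Phase Ia fasted | 74.9/41.1 = 1.82 | 2.03 (1.02 to 4.06) | 25/11.8 = 2.12 | 2.30 (1.28 to 4.15) |
| Phase IIa fed / Phase Ia fasted | 39.5/41.1 = 0.96 | 1.00 (0.53 to 1.90) | 14.3/11.8 = 1.21 | 1.24 (0.72 to 2.14) |
| Phase Ia non-fasted / Phase IIa fed | 74.9/39.5 = 1.90 | 2.02 (1.27 to 3.24) | 25/14.3 = 1.75 | 1.86 (1.25 to 2.76) |

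The AUC result in the first row depends on the method. An approximate 95% interval for the ratio of arithmetic means, 1.82 × exp(±1.96 × √((30.1/74.9)²/5 + (27.5/41.1)²/6)), is 0.96 to 3.46 and includes 1.

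The third row is the warning. Two groups that were not fasted differ about as much as non-fasted and fasted do within Phase Ia. The Phase Ia contrast therefore cannot be read as a settled food effect.

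**Step 3: who can still be affected?**

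Phase Ia enrolment was complete by 1 October 2014 (Section 1.1). The DLT window was 35 days (Section 10.2.1). Full PK profiles end at Cycle 2 Day 2, apart from samples tied to FES-PET scans or adverse events (Section 11.4.1, Appendix 1). Only patients still on treatment can be affected now.

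**The case against.** The strongest defence is that the structure already answers the question. Section 10.3 is general, Section 10.3.1 is the Phase Ia subsection, Table 7 refers back to it, and Appendix 1 omits the meal wording that Appendices 2 to 4 carry. A careful site would probably apply fasted morning dosing to a fasted Phase Ia patient. That narrows the conflict. It does not dispose of the Table 4 reminder or supply a rule for non-fasted patients.

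The defence is right about consequences. A reader might infer any of the following, and the documents do not support them:

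- *That the RP2D rests on the fed-to-fasted contrast and is now in doubt.* Sections 1.1 and 1.2 base it on overall safety and tolerability, PK and pharmacodynamic data, and it is already chosen.
- *That the 800 mg level was intolerable because patients were fasted, or would be worse if fed.* The single DLT was in the fasting cohort, but Section 1.1 judges 800 mg doses intolerable without naming a meal condition. It also suggests that dosing soon after a meal may have lowered gastrointestinal toxicity in Phase IIa.
- *That a two-fold food effect is established.* The contrast is unpaired, uses 5 and 6 patients, covers 6 hours for AUC, and is not reproduced in the larger Phase IIa group.
- *That Phase Ia results are misclassified.* Sections 1.1, 1.2 and 3 already report fasted and non-fasted cohorts separately, and Section 15.1 plans descriptive analyses only.

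**Conclusion.** The point holds as an internal contradiction in current text: Phase Ia patients have administration instructions that cannot all be followed, and no precedence is stated. It bears on continuing patients only. Their number is not given and may be small: the median Phase Ia treatment duration was 123 days at 15 April 2016, and this version cites a January 2017 Investigator's Brochure, more than two years after enrolment closed.

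The possible change in exposure runs from about none (AUC0-6 ratio 0.96) to about two-fold (AUC0-6 1.82, Cmax 2.12). This range assumes that unpaired groups from different parts of the study can be compared, and that the Phase Ia non-fasted condition, which is not defined further, resembles dosing soon after a meal. The geometric ratios also assume log-normal exposure. An effect of uncertain size is a reason for one clear instruction. It is not evidence that past Phase Ia findings are wrong.

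**What to change.** Reconcile Sections 10.3, 10.3.1 and 10.4, Table 4, the notes to Table 7, footnote 9 of Appendix 1, and the two matching synopsis paragraphs, so that each continuing Phase Ia patient has one stated meal condition and one time of day. The text should cover fasted, non-fasted and twice-daily patients. State to whom the all-patients rule in Section 10.3 and the Table 4 reminder apply. Which meal condition and time of day apply is for the sponsor to decide.

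The cost is wording in an amendment or a site letter, with no new procedures. A flag in the listings for any Phase Ia patient whose meal condition changed during treatment would be useful but is optional.

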### **10.3.1 Phase Ia**

During Phase Ia, the full prescribed dose of GDC-0810 should be taken by mouth in the morning, after fasting overnight, at approximately the same time each day; food should not be eaten for at least 1 hour after taking GDC-0810. The dosing regimen may be changed if the PK and safety data from the dose escalation suggest that a discontinuous regimen or another dosing frequency (e.g., BID), with or without a fasting requirement, may be preferable for the Phase IIa portion of the study.

#### **PK Week Lead-In**

In Phase Ia, patients enrolled in the dose escalation cohorts will receive a single oral dose of GDC-0810 in the clinic on Day -7 and will return to the clinic for the next 2 consecutive days for PK sample collection. The time of dose administration will be

**GDC-0810—Genentech, Inc.**

76/Protocol GO29642, Version 9

called “0” (zero) hour. If a patient vomits after receiving GDC-0810, this should be recorded in the patient’s Case Report Form (CRF) but the dose should not be repeated.

In Phase Ib and Phase IIa, there will be no Day – 7 to Day 0 PK lead-in period.

### **Continuous Dosing**

In Phase Ia GDC-0810 will be given continuously beginning on Cycle 1 Day 1 in 28-day cycles. During Cycle 1 of the dose escalation, patients will return to the clinic on a weekly basis (Days 8, 15, and 22) for safety evaluation and collection of predose PK samples. On those days, treatment will be administered in the clinic.

Similarly, on Day 1 of every subsequent new cycle of dosing beginning with Cycle 2, study drug will be administered in the clinic following all the assessments as indicated in the Schedule of Activities.

All other doses of GDC-0810 will be administered on an outpatient basis. It is anticipated that some patients may occasionally forget to take a dose of GDC-0810. In those cases, patients should just take the next scheduled dose, without compensating for the missed dose.

#### **10.3.2 Phase IIa**

The full prescribed dose of GDC-0810 should be taken by mouth at approximately the same time each day and within 30 minutes after eating a meal.

#### **10.3.3 Phase Ib**

Palbociclib administration (if applicable): Palbociclib should be taken with food at the same time each day. The capsule should be swallowed whole. The capsules should not be chewed, crushed, or opened. If a dose is missed, patients should just take the next scheduled palbociclib dose, without compensating for the missed dose.

LHRH administration (if applicable): LHRH agonists should be administered monthly by site staff.

### **Continuous Dosing**

In Phase Ib, GDC-0810 will be given continuously beginning on Cycle 1 Day 1 in 28-day cycles. During Cycle 1 of the dose escalation, patients will return to the clinic on a weekly basis (Days 8, 15, and 22) for safety evaluation and collection of predose PK samples. On those days, treatment will be administered in the clinic. Study treatments, palbociclib will be given on Days 1–21 of each cycle and LHRH agonist will be given on Day 1 of each cycle. Evening dosing (*within 30 minutes after dinner or within 30 minutes of the consistently largest meal of the day*) may be initiated to alleviate gastrointestinal symptoms from GDC-0810. However, on Day 28 of Cycles 1, 2, and 3, the dose of GDC-0810 should be taken in the morning to allow trough PK sample collections on Cycle 2 Day 1, Cycle 3 Day 1, and Cycle 4 Day 1.

Similarly, on Day 1 of every subsequent new cycle of dosing beginning with Cycle 2, study treatment will be administered in the clinic following all the assessments as indicated in the Schedule of Activities.

All other doses of GDC-0810 or palbociclib will be administered on an outpatient basis. It is anticipated that some patients may occasionally forget to take a dose of GDC-0810 or palbociclib. In those cases, patients should just take the next scheduled dose, without compensating for the missed dose.

*Palbociclib and GDC-0810 do not have to be taken together; however, each drug should be taken at a consistent time each day.*

